2.3 REGISTRATION PROCEDURES

Authorized staff must register an eligible candidate with NCI Central Registration Office (CRO) within 24 hours of signing consent. A registration Eligibility Checklist from the web site (<http://home.ccr.cancer.gov/intra/eligibility/welcome.htm>) must be completed and sent via encrypted email to: NCI Central Registration Office [contact]. After confirmation of eligibility at Central Registration Office, CRO staff will call pharmacy to advise them of the acceptance of the patient on the protocol prior to the release of any investigational agents. Verification of Registration will be forwarded electronically via e-mail to the research team. A recorder is available during non-working hours.

2.3.1 Treatment Assignment Procedures (For registration purposes only):

Cohorts

Number	Name	Description
1	1	Subjects with advanced biliary tract carcinoma

Arms

Number	Name	Description
1	1	Pembrolizumab + Oxaliplatin + Capecitabine

Arm assignment

Subjects in Cohort 1 will be directly assigned to Arm 1.

2.4 BASELINE EVALUATION

Tests done at screening do not need to be repeated on baseline if performed in designated time frame.

Within 28 days prior to first dose:

- CT or PET of chest, abdomen and pelvis (or MRI abdomen)
- Electrocardiogram
- HLA phenotype (any time prior to first dose)
- Optional tumor biopsy for research

Within 7 days prior to first dose:

- History and physical exam with vital signs

Within 72 hours prior to first dose:

[figure not shown]
- Serum or urine pregnancy test for female participants of childbearing age (in the absence of prior hysterectomy).

3 STUDY IMPLEMENTATION

3.1 STUDY DESIGN

The proposed study is a phase II study of Pembrolizumab in combination with CAPOX in patients with advanced biliary tract carcinoma.

Group	N	PEMBROLIZUMAB	CapOx
Previously treated BTC	19	Day 1: Pembrolizumab 200mg IV, 30 minutes. q-3-weekly until PD	Day 1: Oxaliplatin 130mg/m ² IV over 2 hours Days 1–14: Capecitabine 750 mg/m ² twice daily PO. q-3-weekly for 18 weeks

3.2 SCHEDULE

Pembrolizumab and Oxaliplatin should be administered on Day 1 of cycles 1-6. Pembrolizumab should be infused first and Oxaliplatin should be given at least 30 minutes after Pembrolizumab.

Capecitabine should be administered orally with first dose the evening of Day 1 of cycles 1-6 and last dose the morning of day 14 of cycles 1-6, given as intermittent treatment.

Cycle length is 3 weeks (consisting of 2 weeks of capecitabine treatment followed by 1 week without capecitabine treatment).

Starting in cycle 7, Pembrolizumab should be administered alone on Day 1, continuing once every 3 weeks until disease progression.

Each cycle may start up to 3 days before or after the scheduled Day 1 due to administrative reasons.

3.3 DRUG ADMINISTRATION

3.3.1 Pembrolizumab

Pembrolizumab 200 mg will be administered as a 30-minute IV infusion on Day 1 of each cycle. Every effort should be made to target infusion timing to be as close to 30 minutes as possible. However, a window of -5 minutes and +10 minutes is permitted (i.e., infusion time is 25 – 40 mins). Please see section **11.1.2** for preparation instructions.

3.3.2 CAPOX

Capecitabine should be administered at a dose of 750 mg/m² PO every 12 hours (+/- 4 hours window is allowed) (equivalent to a total daily dose of 1500 mg/m²). Doses will be rounded downward to the nearest 150 mg. Patients will begin Capecitabine dosing on the first day of cycles 1-6 and will continue to receive Capecitabine for 14 days. Patients will be instructed to take Capecitabine with food. No morning dose should be taken on day 1 of the cycle and no

evening dose should be taken on day 14 of the cycle. Patients will complete and return Patient's Diary ([Appendix C](#)).

Oxaliplatin should be administered on D1 of cycles 1-6 at a dose of 130mg/m² IV Infusion in 500mls Glucose 5% over 2 hours. Please see section [11.2.3](#) for preparation instructions.

Premedication with ondansetron 8mg and dexamethasone 8mg will be given 15-30 mins prior to infusion.

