3.5 STUDY CALENDAR

	Screening	Baseline	Cycles 1-6⁵	Cycle 7- to PD⁵	EOT⁹	Follow Up¹⁰
Pembrolizumab ¹			X	X		
Oxaliplatin ²			X			
Capecitabine ³			X			
Informed consent	X					
Medical history ⁴	X	X				
Concomitant meds			X	X		
Adverse event evaluation			X	X	X	
Physical exam ⁴	X	X	X	X	X	
Vital signs ⁴	X	X	X	X	X	
Height	X					
Weight ⁴	X		X	X		
Performance Status ⁴	X		X	X	X	
CBC w/differential, Platelets ⁴	X		X ¹³	X ¹³	X	
PT, INR, PTT, Fibrinogen			X ¹³	X ¹³	X	
Serum chemistry ^{4, 12}	X		X ¹³	X ¹³	X	
HIV, Hepatitis B and C serology and/or viral load	X					
HLA		X				
Thyroid Panel			X ¹³	X ¹³	X	
TB testing (if clinically indicated)	X					
Serum or urine pregnancy test ⁴	X	X				

	Screening	Baseline	Cycles 1-6 ⁵	Cycle 7- to PD ⁵	EOT ⁹	Follow Up ¹⁰
Tumor markers: aFP, CEA or Ca 19.9 ⁴			X ¹³	X ¹³		
EKG ⁴	X	X				
Confirmation of dx by NCI LP	X					
Restaging radiologic Evaluation ⁴	X	X	X ⁶	X ⁶		
Optional Tumor biopsy		X	X ⁷			
Immune monitoring ¹¹			X	X		
Blood for TCR beta sequencing ¹⁴			X	X		
Advance Directive ⁸		X				
Annual telephone contact						X

¹ 200 mg of Pembrolizumab will be administered as a 30-minute IV infusion Day 1 of each cycle.

² Oxaliplatin will be administered on D1 of each cycle at a dose of 130mg/m² IV

³ Capecitabine will be administered at a dose of 750 mg/m² PO every 12 hours. Doses will be rounded downward to the nearest 150 mg. Patients will begin Capecitabine dosing on the Day 1 of each cycle and will continue to receive Capecitabine for 14 days.

⁴ Tests performed at screening do not need to be repeated on baseline or Cycle 1 Day 1 if performed in designated time frame

⁵ Each cycle is 21 days. Trial treatment may be administered up to 3 days before or after the scheduled Day 1 of each cycle due to administrative reasons.

⁶ CT/PET/MRI of chest abdomen and pelvis. Restaging scans every 9 weeks +/- 7 days.

⁷ Performed on cycle 3 Day 1 only +/- 7 days

⁸ As indicated in section **10.3**, all subjects will be offered the opportunity to complete an NIH Advance Directive form. This should be done preferably at baseline but can be done at any time during the study as long as the capacity to do so is retained. The completion of the form is strongly recommended but is not required.

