13.3 APPENDIX C PATIENT'S MEDICATION DIARY _____

Cycle _____

Patient's ID _____

INSTRUCTIONS TO THE PATIENT:

1. Complete one form for each cycle of treatment
2. You will take capecitabine _____ mg twice a day. You should take the tablets with food at approximately the same time each day.
3. Dose: _____ 150 mg _____ 500 mg
4. Record the date, the number of tablets that you took, and when you took them.
5. If you have any comments or notice any side effects, please record them in the comments column.
6. Please bring this form and your bottles of capecitabine when you come for your clinic visits.

Day	Date	Time of AM Dose	# of Tablets Taken		Time of PM Dose	# of Tablets Taken		Comments
			150 mg	500mg		150 mg	500mg	
1								
2								
3								
4								
5								
6								
7								
8								
9								
10								
11								
12								
13								
14								

Patient's signature: _____

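### The capecitabine diary does not carry the first- and last-dose rule of Sections 3.2 and 3.3.2, so a patient relying on it could take up to two excluded doses per cycle

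*Combined protocol and SAP*

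**What the plan says.** Five places in the protocol describe the capecitabine course.

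- **Section 3.2 (Schedule)** fixes both ends: "first dose the evening of Day 1 of cycles 1-6 and last dose the morning of day 14 of cycles 1-6". It then describes the three-week cycle as "consisting of 2 weeks of capecitabine treatment followed by 1 week without capecitabine treatment".
- **Section 3.3.2 (CAPOX)** gives 750 mg/m² every 12 hours, equated to 1500 mg/m² per day, for 14 days. In the same paragraph it adds "No morning dose should be taken on day 1 of the cycle" and likewise excludes the evening dose on day 14. The next sentence refers patients to the diary in Appendix C, which they are to complete and return.
- **Section 3.1 (design table)** has "Capecitabine 750 mg/m ² twice daily PO" against Days 1–14, with no exception.
- **Section 3.5 (calendar footnote 3)** has dosing every 12 hours from Day 1 and says patients "will continue to receive Capecitabine for 14 days", again with no exception.
- **Appendix C (patient diary)** tells the patient to take a stated number of milligrams twice a day, and adds "You should take the tablets with food at approximately the same time each day". The grid has a row for each day from 1 to 14, with morning and evening columns in every row. None of its six numbered instructions mentions an omitted first or last dose.

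**The concern.** The diary is the patient's own dosing sheet for each cycle. Section 3.3.2 excludes two specific doses and then sends the patient to a form that, as worded, provides for both. Taken alone, the form reads as two doses on each of 14 days.

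What is at stake is whether the patient form agrees with the administration section. A patient who follows the form literally could take a Day 1 morning dose and a Day 14 evening dose that Section 3.3.2 says not to take. The mismatch recurs in each of the six capecitabine cycles.

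**Working it through.** **Inputs**

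- Unit dose 750 mg/m² every 12 hours (Section 3.3.2 and calendar footnote 3).
- First dose on the evening of Day 1, last dose on the morning of Day 14 (Section 3.2; the same two exclusions in Section 3.3.2).
- Diary grid of 14 rows with a morning and an evening column (Appendix C).
- Six capecitabine cycles (Section 3.2).

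**Step 1. Reproduce the plan's own figure.** 2 × 750 = 1500 mg/m² per day, as Section 3.3.2 states. The documents give no number of doses per cycle, so the counts below are derived.

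**Step 2. Doses under Sections 3.2 and 3.3.2.** One on Day 1, two on each of Days 2–13, one on Day 14:

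1 + (12 × 2) + 1 = 26 doses; 26 × 750 = 19,500 mg/m² per cycle.

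**Step 3. Slots in the diary grid.**

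14 × 2 = 28 slots; 28 × 750 = 21,000 mg/m² per cycle if every slot is used.

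**Step 4. Difference.**

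28 − 26 = 2 doses; 2 × 750 = 1,500 mg/m² per cycle; 2/28 = 7.1%.

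The two slots that differ are Day 1 morning and Day 14 evening, which are the two doses Section 3.3.2 excludes. If both were taken in all six cycles, the excess would be 12 doses, or 9,000 mg/m². That is an upper bound. All these figures are nominal: they ignore rounding down to the nearest 150 mg (Section 3.3.2) and any dose reduction under Sections 3.4.3 and 3.4.4.

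**Step 5. Does the 14-day wording itself conflict?** Evening Day 1 to morning Day 14 puts at least one dose on each of 14 calendar days, so a 14-day or two-week description fits. It would conflict only if it meant 14 full daily doses: 28 twelve-hourly doses starting on the evening of Day 1 would end on the morning of Day 15. No section says that it means this.

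**The case against.** The strongest reply is that the operative rule is clear. Only Sections 3.2 and 3.3.2 address the first and last doses, and they agree. In both, the general duration stands beside the specific rule that qualifies it. The design table and calendar footnote are summaries. Footnote 2, next to footnote 3, is abbreviated in the same way: it gives oxaliplatin on Day 1 of each cycle, although the calendar grid and Section 3.2 confine it to cycles 1–6. This stands. A reader might infer that the planned dose per cycle has two values; the documents do not support that.

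A reader might also infer that adherence would be mis-scored, with 26 doses counted as two missed or 28 as two extra. Section 8 defines no diary-based adherence score and no dose-intensity analysis, so that consequence has no basis in the plan.

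On the diary, the reply is that the grid is for recording, that an empty box is not an instruction, and that staff may explain the rule in person. Shading of the two cells could also have been lost when the form was extracted as text. These points limit the claim: the form permits the two doses, but it does not follow that patients take them. They do not remove the problem, because the diary also gives a written twice-daily instruction without exception, and shading would not change that wording.

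**Conclusion.** The point holds as a low-severity inconsistency between the patient form and the administration sections. Sections 3.2 and 3.3.2 give 26 doses per cycle. The diary provides 28 slots under an unqualified twice-daily instruction. A patient relying on the form could take up to two excluded doses per cycle, nominally 1,500 mg/m² or 7.1% of the 28-dose total.

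This assumes a full starting dose, no rounding, and no verbal or other written instruction that overrides the form; the consent form is not among the documents read. The design table and calendar footnote 3 are worth aligning at the same time, but on their own they can be read as shorthand.

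The Simon two-stage design, its decision boundaries and the 5-month progression-free endpoint are unaffected. Which first and last dose is intended is for the clinical team to state.

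**What to change.** Reconcile Section 3.1, Section 3.2, Section 3.3.2, calendar footnote 3 and Appendix C on one explicit first dose and last dose per cycle, as the clinical team intends. Then make both the diary's written instructions and its grid match, for example by blocking out any box in which no dose is to be taken. The cost is a few wording changes and a reissued diary form. No statistical text, sample size or analysis changes.

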3.4 DOSING DELAYS AND MODIFICATIONS

3.4.1 General guidance

If, in the opinion of the investigator, a toxicity is considered to be due solely to one drug (e.g. hand-foot syndrome secondary to capecitabine, neurotoxicity due to oxaliplatin), the dose of the other drug does not require modification.

When, at the beginning of a treatment cycle, treatment delay related to either oxaliplatin or capecitabine treatment alone is indicated, both oxaliplatin and capecitabine treatment should be delayed (except in the case of oxaliplatin-related neurological adverse events). Treatment should only be restarted when the requirements for restarting both oxaliplatin and capecitabine are met, or when oxaliplatin has to be discontinued but the requirements for restarting capecitabine alone are met.

Dose modifications for isolated abnormal hematologic lab values will be based on hematological parameters at start of a treatment cycle. There is no scheduled sampling during a treatment cycle and thus, no scheduled collection of nadir values.

If capecitabine must be discontinued permanently due to toxicity, the patient may continue on oxaliplatin alone. If the patient has SD or better on study, and both capecitabine and oxaliplatin are stopped prematurely for toxicity, the PI may consider continuing pembrolizumab.

3.4.2 Dose Modifications for Hematologic Toxicity

Capecitabine is not expected to worsen or unduly prolong episodes of neutropenia/granulocytopenia. The next treatment cycle can only start if hematologic toxicity has recovered to grade ≤ 1 . No dose reductions or interruptions will be required for anemia (non-hemolytic) as it can be satisfactorily managed by transfusions.

3.4.3 Dose Modifications for Neutropenia for Capecitabine and Oxaliplatin

	Grade 2 1.0 \leq ANC $<$ 1.5 x 10 ⁹ /L Platelets $>$ 50 - $<$ 75 x 10 ⁹ /L	Grade 3 0.5 \leq ANC $<$ 1.0 x 10 ⁹ /L Platelets $>$ 10 - $<$ 50 x 10 ⁹ /L	Grade 4 ANC $<$ 0.5 x 10 ⁹ /L Platelets $<$ 10 x 10 ⁹ /L
1st occurrence	No dose adjustment	Capecitabine 75% of original dose + oxaliplatin 100 mg/m ²	Capecitabine 50% of original dose + oxaliplatin 85 mg/m ²
2nd occurrence	No dose adjustment	Capecitabine 75% of original dose + oxaliplatin 85 mg/m ²	Stop treatment permanently
3rd occurrence	No dose adjustment	Stop treatment permanently unless it is in the best interest of the patient to treat with	Not applicable

	Grade 2 1.0 \leq ANC $<$ 1.5 \times 10 ⁹ /L Platelets $>$ 50 - $<$ 75 \times 10 ⁹ /L	Grade 3 0.5 \leq ANC $<$ 1.0 \times 10 ⁹ /L Platelets $>$ 10 - $<$ 50 \times 10 ⁹ /L	Grade 4 ANC $<$ 0.5 \times 10 ⁹ /L Platelets $<$ 10 \times 10 ⁹ /L
		capecitabine monotherapy at 75% of original dose	

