3.4.4 Capecitabine

Given that capecitabine is an FDA-approved agent, dose adjustments and management will be as per standard of care, as outlined in the package insert. Capecitabine will be withheld in cases of Grade 2 or greater hand-foot syndrome or mucositis that do not respond to medical management. Capecitabine will be restarted after the symptoms improved to Grade 1. The dose of Capecitabine may be adjusted in the event of recurrent Grade 2 or greater hand-foot syndrome, neutropenia, or other Capecitabine toxicities that have not been attributed to other study agents.

Summary of management of common Capecitabine toxicities	
Toxicity	Capecitabine dose modification
Grade 2 hand foot syndrome	Interrupt until \leq grade 1. May then restart capecitabine at full dose. For second occurrence, hold capecitabine until \leq grade 1, then restart capecitabine one dose level lower (75% of starting dose first occurrence, 50% of the starting dose the second occurrence, discontinue the third occurrence).
Grade 3 hand foot syndrome	Interrupt until \leq grade 1. Then restart capecitabine one dose level lower (75% of starting dose first occurrence, 50% of the starting dose the second occurrence, discontinue the third occurrence).

*Dose reductions for capecitabine

1. Starting dose
2. 75% of the starting dose
3. 50% of the starting dose

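### Read literally, the table in section 3.4.3 can raise a reduced dose after renewed blood-count toxicity, because it does not say that an earlier reduction is kept

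*Combined protocol and SAP*

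**What the plan says.** Section 3.4.3 gives one table for neutrophil and platelet counts, with grade in the columns and occurrence in the rows. The cells that matter here are:

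- Grade 4, first occurrence: "Capecitabine 50% of original dose + oxaliplatin 85" mg/m². A second occurrence ends treatment.
- Grade 3, first occurrence: "Capecitabine 75% of original dose + oxaliplatin 100" mg/m².
- Grade 3, second occurrence: "Capecitabine 75% of original dose + oxaliplatin 85" mg/m².
- Grade 3, third occurrence: stop, or capecitabine alone at 75% if that is judged best for the patient.

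The capecitabine percentages refer to the original dose, not the dose the patient is taking.

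The surrounding text adds four things:

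- Section 3.4.1 sets the timing: "Dose modifications for isolated abnormal hematologic lab values will be based on hematological parameters at start of a treatment cycle".
- Section 3.4.1 also says that when a toxicity is judged to come from one drug only, "the dose of the other drug does not require modification".
- Section 3.4.2 says "Capecitabine is not expected to worsen or unduly prolong episodes of" neutropenia, and requires recovery to Grade 1 or better before the next cycle.
- Section 3.4.4 says, for capecitabine, that "dose adjustments and management will be as per standard of care, as outlined in the package insert", and adds: "The dose of Capecitabine may be adjusted in the event of recurrent Grade 2 or greater hand-foot syndrome, neutropenia" or other toxicities not attributed to other study agents.

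Sections 3.4.1 to 3.4.4 do not say whether a dose reduced for a blood count stays reduced, or whether occurrences are counted within one grade or across grades.

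**The concern.** A dose-reduction table should not lead to a higher dose when toxicity recurs. Here the Grade 4 column cuts deeper than the Grade 3 column, and each cell is an absolute dose. A patient who has a Grade 4 count and later a Grade 3 count therefore meets a cell that names more drug than the patient is receiving.

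The stakes are individual safety and consistent conduct. An investigator who follows the cell gives the higher dose to a patient with two severe counts. Another investigator, who reads the table as setting upper limits, keeps the lower dose. The text does not settle which of them is right.

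**Working it through.** The plan states no figure on this point to reproduce. The check reads the cells for the sequence Grade 4, then Grade 3, and works out the doses.

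**Inputs.** Capecitabine starts at 750 mg/m² every 12 hours, rounded down in steps of 150 mg (section 3.3.2). It runs from the evening of day 1 to the morning of day 14 in cycles 1–6 (section 3.2). Oxaliplatin starts at 130 mg/m² (section 3.3.2). The cells are those of section 3.4.3.

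**Step 1: which cell applies to the later Grade 3 count?**

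| How occurrences are counted | Cell reached | Capecitabine | Oxaliplatin (mg/m²) |
|---|---|---|---|
| Within grade, no earlier Grade 3 | Grade 3, first | 50% → 75% | 85 → 100 |
| Within grade, one earlier Grade 3 | Grade 3, second | 50% → 75% | 85 → 85 |
| Across grades, Grade 4 was first | Grade 3, second | 50% → 75% | 85 → 85 |

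Under across-grade counting, a Grade 4 count that is not the first event ends treatment, so the rise needs Grade 4 to come first. In the reverse order (Grade 3, then a first Grade 4 under within-grade counting) capecitabine falls from 75% to 50%. Within a single grade column no dose ever rises.

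**Step 2: size per dose.**
- Capecitabine after Grade 4: 0.50 × 750 = 375 mg/m².
- Capecitabine after the later Grade 3: 0.75 × 750 = 562.5 mg/m².
- Rise: 187.5 mg/m², and 187.5 / 375 = 50%. The raised dose is still 25% below the start.
- Oxaliplatin: 100 − 85 = 15 mg/m², and 15 / 85 = 17.6%. Since 100 / 130 = 0.77, it is still 23% below the start.

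Rounding changes the capecitabine percentage in either direction. The body surface areas below are assumed, and rounding is taken to apply to reduced doses too:
- At 2.0 m², 750 mg stays 750 and 1,125 becomes 1,050, a rise of 40%.
- At 1.9 m², 712.5 becomes 600 and 1,068.75 becomes 1,050, a rise of 75%.

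**Step 3: size per patient, before rounding.** Doses per cycle are 1 + 12 × 2 + 1 = 26, so the rise is 26 × 187.5 = 4,875 mg/m² per cycle. The earliest case is Grade 4 at the start of cycle 2 and Grade 3 at the start of cycle 3, which leaves cycles 3–6. The range is 1 to 4 cycles: 4,875 to 19,500 mg/m² of capecitabine and, where it applies, 15 to 60 mg/m² of oxaliplatin. The upper ends assume no further modification.

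**Step 4: does attribution to one drug close the gap?** There are 3⁵ = 243 patterns of no severe count, Grade 3 or Grade 4 over the starts of cycles 2–6. A third Grade 3 is taken as a stop, and Grade 2 is left out of the counting. The table gives the number of patterns with a rise (capecitabine / oxaliplatin):

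| Reading of the later Grade 3 count | Within grade | Across grades |
|---|---|---|
| Table alone | 82 / 58 | 58 / 0 |
| Attributed to oxaliplatin only, capecitabine unchanged | 0 / 58 | 0 / 0 |
| Attributed to capecitabine only, oxaliplatin unchanged | 82 / 0 | 58 / 0 |
| With the footnote proposed below | 0 / 0 | 0 / 0 |

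These are counts of patterns, not probabilities. Attribution removes every rise only when the count is put down to oxaliplatin and occurrences are counted across grades.

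**The case against.** The strongest reply is that the table is silent, not wrong. Its cells are cuts from the original dose, section 3.4.4 lists the capecitabine levels in descending order as reductions, and few clinicians would treat such a cell as an order to give more drug after more toxicity. That is fair. A reader might infer that the protocol instructs escalation. It does not: no sentence says to raise a dose, and the rise appears only when the cells are read literally.

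A reader might also infer that the capecitabine rise is automatic. The documents do not support that either. Section 3.4.2 points away from capecitabine as the cause of neutropenia, and section 3.4.1 then allows capecitabine to stay at 50%. This reply has limits: the section 3.4.1 wording is permissive, section 3.4.2 speaks of neutropenia while the table also covers platelets, and the oxaliplatin cell still applies.

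Nor can it be said that the plan has no rule at all for capecitabine. The package-insert reference in section 3.4.4 is worded as mandatory and may bar re-escalation. Its content is not in the documents, so this cannot be checked. The reference does not cover oxaliplatin, and if the insert does bar re-escalation, it conflicts with an explicit cell.

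The remaining safeguards are general. Section 4 appeals to clinical judgment, and section 3.6.1 allows removal for unacceptable toxicity, for recovery delayed beyond 28 days, or at the investigator's discretion. These allow the lower dose or a stop. They do not set the dose if treatment continues.

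**Conclusion.** The point holds as a conditional one. Taken literally, section 3.4.3 can raise capecitabine nominally from 375 to 562.5 mg/m² per dose after a Grade 4 and then a Grade 3 count, under either way of counting. It can raise oxaliplatin from 85 to 100 mg/m² only under within-grade counting with no earlier Grade 3. The capecitabine part falls away if the count is attributed solely to oxaliplatin and capecitabine is left unchanged, or if the package insert bars re-escalation.

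The point is minor. The sequence is probably rare, though the documents give no basis for a frequency. Section 8 caps accrual at 19 patients. A reader might look for an effect on the trial's conclusion, but the 5-month progression-free decision rule in section 8 does not depend on this table. That the cells name these doses is certain. How often an investigator would act on them is not known.

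**What to change.** Add a footnote to the table in section 3.4.3:

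> If the tabulated dose of capecitabine or oxaliplatin is higher than the patient's current dose, keep the current (lower) dose; doses reduced for hematologic toxicity are not re-escalated.

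This works under either counting rule and any attribution, and it covers oxaliplatin as well as capecitabine. It costs one line in the next amendment. It needs no extra visits, tests or patients, and leaves the starting doses and the analysis as they are.
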